1. INTRODUCTION

The MCP-103-205 study is a multicenter, randomized, double-blind, placebo-controlled, parallel-group, dose-range-finding, 12-week study, consisting of 4 distinct periods: up to 2 weeks Screening, 2-3 weeks Pretreatment, 12 weeks Treatment, and 2 weeks Posttreatment. The study will enroll approximately 368 patients who have IBS-D diagnosed using Rome IV criteria. Eligible patients will be randomized in equal proportions to 1 of 4 treatments: 300, 600, or 1200 µg of MD-7246, or matching placebo, administered once daily. MD-7246 is a delayed release (DR) tablet formulation of linaclotide designed to release linaclotide in the distal ileum near the ileocecal junction, to target guanylate cyclase C (GC-C) receptors in the colon and minimize secretory effects in the gastrointestinal (GI) tract.

This statistical analysis plan (SAP) describes the statistical analysis methods for the analysis of efficacy and safety data collected according to the following documents:

- Study Protocol MCP-103-205 Amendment 1, dated 29 January 2019
- Case Report Form (CRF) version 3.0, dated 26 November 2019

Data presentation details for the analyses included in this SAP will be specified in a separate data presentation plan for the format of Tables, Figures and Listings.

2. STUDY OBJECTIVES

The objectives of this study are to evaluate the safety and tolerability, treatment effect on abdominal pain, and dose response of MD-7246 administered orally to patients with diarrhea-predominant irritable bowel syndrome (IBS-D). An exploratory objective of the study is to assess bowel function changes with MD-7246 in patients with IBS-D.

3. STUDY DESIGN

3.1. General Description

This is a multicenter, randomized, double-blind, placebo-controlled, parallel-group, dose-range-finding, 12-week study, consisting of 4 distinct periods, as illustrated in [Figure 1](#) below. The study will enroll patients who have IBS-D diagnosed using Rome IV criteria. Eligible patients will be randomized in equal proportions to 1 of 4 treatments: 300, 600, or 1200 µg of MD-7246, or matching placebo, administered once daily. MD-7246 is a delayed release (DR) tablet formulation of linaclotide designed to release linaclotide in the distal ileum near the ileocecal junction, to target guanylate cyclase C (GC-C) receptors in the colon and minimize secretory effects in the gastrointestinal (GI) tract.

Study Periods

Screening Period: The Screening Period starts with the signing of the informed consent form (ICF; Appendix 1) and may last for up to 28 days. During this period, patient eligibility for entry into the Pretreatment Period will be determined. Loperamide, a protocol-permitted over-the-counter (OTC) medication for diarrhea, will be distributed to eligible patients beginning at the Screening Visit. The end of the Screening Period coincides with the start of the Pretreatment Period. If the patient meets the entry criteria assessed at the Screening Visit and does not require a washout of prohibited medicines, the Screening Visit and Pretreatment Visit may be combined into one visit.

Pretreatment Period: The Pretreatment Period is defined as the 14 to 21 days immediately before the Randomization Visit. During this period, patients will provide the following information in a handheld electronic diary (eDiary):

- Daily Assessments:
 - Daily Abdominal Symptom Assessments in a daily evening report
 - Bowel Movement (BM)-related Assessments on an event-driven basis (meaning these are assessments made for each event at the time the event occurs [or during the daily evening report for any events not previously entered for that day])
- Weekly Assessments:
 - Weekly Patient Assessment of Degree of Relief of IBS Symptoms
 - Weekly Patient Assessment of Adequate Relief of IBS Pain
 - Weekly Patient Assessment of BM-related Symptom Severity (patient global impression of severity [PGI-S])
 - Weekly Patient Assessment of BM-related Symptom Change (patient global impression of change [PGI-C])
- Use of Loperamide for Diarrhea on an event-driven basis

Patients who satisfy all entry criteria will enter the Treatment Period.

Treatment Period: The Treatment Period begins with treatment assignment and lasts for 12 weeks. Patients will be randomized in equal proportions to 1 of 4 treatments: 300, 600, or 1200 µg of MD-7246, or matching placebo. Patients will take their initial dose of study drug at the study center during the Randomization Visit. On all other days, study drug will be taken once daily at approximately the same time of day without regard to food (patients will be instructed to choose a time that is convenient for them and continue daily dosing at that time throughout the Treatment Period). Patients will continue to use the handheld eDiary to provide their:

- Daily Assessments:
 - Daily Abdominal Symptom Assessments in a daily evening report
 - BM-related Assessments on an event-driven basis
- Weekly Assessments:
 - Weekly Patient Assessment of Degree of Relief of IBS Symptoms
 - Weekly Patient Assessment of Adequate Relief of IBS Pain
 - Weekly Patient Assessment of Treatment Satisfaction
 - Weekly Patient Assessment of BM-related Symptom Severity (PGI-S)
 - Weekly Patient Assessment of BM-related Symptom Change (PGI-C)
- Use of Loperamide for Diarrhea on an event-driven basis

Health-related quality-of-life and patient-outcome assessments will be performed at the Randomization Visit and at study visits throughout the Treatment Period. A list of these assessments and the visits when they will be performed is provided in the [Schedule of Evaluations](#).

Patients will complete a Week 2 Phone Call, and Week 4, Week 8, and Week 12/End of Treatment (EOT) Visits during the Treatment Period (see [Schedule of Evaluations](#)).

[figure not shown]
Posttreatment Period: The Posttreatment Period starts on the day following the last day of dosing (Week 12/EOT Visit) and finishes 2 weeks later at the End of Study (EOS) Follow-up Phone Call. During the call, patients will be asked to report any AEs and medicines taken since the Week 12/EOT Visit and detail any other symptoms or comments they may have (at the discretion of the investigator, patients may be requested to return to the study center for their EOS Follow-up).

Overall Study Stopping Criteria and Data Monitoring Committee

The Sponsor may stop enrollment prematurely because of low recruitment rates. The Sponsor may suspend or terminate the study prematurely because of a change in opinion of the Institutional Review Board, Data Monitoring Committee (DMC), or a regulatory authority decision.

An independent DMC will regularly review safety data during the conduct of the study. Periodic safety review meetings will be scheduled when approximately 1/3 and 2/3 of patients have been randomized. The committee will review accumulated safety data, and may request unblinding of the treatment groups, in order to make any recommendations regarding the acceptability of continuing the study based on AEs reported.

Figure 1: Overview of Study Design

3.2. Discussion of Study Design, Including Choice of Control Group

A double-blind, placebo-controlled, parallel-group study design was chosen in accordance with the concepts in ICH E10, Choice of Control Groups and Related Issues in Clinical Trials, in order to provide comparable treatment groups and minimal chance of selection or investigator bias. The study has a 14-21 day Pretreatment Period to establish patient baseline values without study drug and to familiarize patients with data collection methodology (ie, eDiary), a 12-week Treatment Period to compare the test treatment to a placebo control, and a 2-week Posttreatment Period to assess safety after MD-7246 treatment has been withdrawn.

The study will evaluate the effect of the test treatment on abdominal pain in IBS-D patients. Because the test treatment is not expected to significantly affect bowel function, loperamide will be provided beginning at the Screening Visit for patients to use as needed, at the patients' discretion, to stabilize their diarrhea throughout the study; utilization of loperamide for diarrhea will be recorded on an event-driven basis.

Three doses of MD-7246 were selected to assess the relationship between dose and response.

3.3. Treatments Administered

The Treatment Period begins with treatment assignment and lasts for 12 weeks. Patients will be randomized in equal proportions to 1 of 4 treatments: 300, 600, or 1200 µg of MD-7246 or matching placebo. Patients will take their initial dose of study drug at the study center during the Randomization Visit. On all other days, study drug will be taken once daily at approximately the same time of day without regard to food (patients will be instructed to choose a time that is convenient for them and continue daily dosing at that time throughout the Treatment Period).

3.4. Methods of Assigning Subjects to Treatment Groups

Patients who meet all of the inclusion criteria and none of the exclusion criteria will be randomized into the study at the Randomization Visit on Day 1. Approximately 368 patients will be randomized to 1 of 4 treatments: MD-7246 300 µg, 600 µg, or 1200 µg or placebo (1:1:1:1). Randomization numbers will be assigned by interactive web response system (IWRS).

3.5. Blinding

This is a double-blind study. The Sponsor study personnel, the investigator, all other site study personnel, and the patient will remain blinded to individual patient treatment assignments throughout the study. Specifically designated personnel in the Global Patient Safety (GPS) group at Ironwood may be unblinded to the treatment assignment of individual patients for regulatory reporting purposes.

Patient randomization codes for the Treatment Period will be generated by Allergan and implemented by the IWRS vendor (an electronic version will be stored on a secure server). The randomization list will identify each patient by randomization number and include the patient's corresponding treatment assignment. The medication code list will be supplied by [REDACTED] to the IWRS vendor.

In case of an emergency, the IWRS will be accessed to obtain the study drug assignment of a patient. Accessing the IWRS for emergency unblinding should be done only in an emergency that necessitates identifying the treatment assignment for the welfare of the patient, and only after unsuccessfully attempting to contact the Medical Monitor, or designee. If the blind is broken, the study center will notify the Sponsor immediately. An explanation for breaking the blind will be recorded on the relevant eCRF. Breaking the blind at the study center will disqualify the patient from further participation in the study (refer to Protocol Section 6.3 for details regarding procedures and follow-up for patients who are discontinued from therapy).

4. DETERMINATION OF SAMPLE SIZE

In a previously conducted Phase 2b trial utilizing MD-7246 (ie, Study MCP-103-204), the observed sample standard deviation (SD) for the change from baseline to Week 12 in abdominal pain at its worst ranged from 2.32 to 2.88. Assuming a clinically meaningful treatment difference between MD-7246 and placebo of 1.0 for the mean change from baseline to Week 12 in abdominal pain at its worst, an SD of 2.4, and 92 patients per treatment group (368 patients total), the estimated power is approximately 80% to detect a difference between each MD-7246 dose and placebo at a 2-sided significance level of 0.05 using a 2-sample t-test.

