- Patient Assessment of BM-related Symptom Change on a 7-point ordinal scale

Study Visit Assessments:

- The following information will be captured in the eDiary at the Pretreatment Visit:
 - Pain Catastrophizing Scale
- The following information will be captured in the eDiary at the Randomization Visit before the first dose of study drug and at all subsequent study visits:
 - Short Form-12 Health Survey version 2 (SF-12v2)
 - EuroQol-5 Dimension (EQ-5D-3L)
 - Irritable Bowel Syndrome-Symptom Severity Scale (IBS-SSS)

Protocol-permitted OTC Medication for Diarrhea

- Throughout the study (Screening Period through Posttreatment Period), patients will be allowed to use loperamide (Imodium[®]) to assist in the management of their diarrhea. Loperamide will be provided to the patient at study visits to use as needed (at the patient's discretion) to stabilize their diarrhea throughout the study. Beginning at the Pretreatment Visit (when the patients receive the eDiary) through the Week 12/EOT Visit, the day (yesterday/today) and dose will be entered by the patient for each use of loperamide for diarrhea on an event-driven basis.
- Prescription medications for the treatment of diarrhea or IBS are not permitted during the study, from 4 weeks (28 days) before the Pretreatment Visit (or 3 months before the Pretreatment Visit for rifaximin) through the EOS Follow-up Phone Call (see [Appendix 2](#)).

Number of Patients:

Approximately 368 IBS-D patients (approximately 92 patients per treatment group) will be randomized into the Treatment Period.

Diagnosis and Main Criteria for Inclusion:

Inclusion Criteria

To be eligible to participate in the study, patients must meet all of the following criteria:

1. Patient has given consent by signing an ICF.
2. Patient is an ambulatory male or female aged 18 years or older at the Screening Visit.
3. Female patients are not pregnant and lactating females must agree not to breastfeed.
4. Female patients of childbearing potential (ie, women who are not postmenopausal or who have not had a bilateral oophorectomy, hysterectomy, or tubal ligation) who are sexually active with a male partner must agree to use one of the following methods of birth control from the date they sign the ICF until the End of Study Visit:
 - a. Hormonal contraception (ie, oral contraceptive, contraceptive implant, or injectable hormonal contraceptive)
 - b. Double-barrier birth control (eg, condom plus intrauterine device, diaphragm plus spermicide)

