6.4 REPLACEMENT PROCEDURES

Patients in this study who prematurely discontinue treatment will not be replaced.

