7.3. Handling of Dropouts/Missing Data Imputation Method

For weekly responder endpoints based on daily eDiary entries (eg, Weekly Abdominal Pain 30% Responder), a patient who reported daily assess for fewer than 4 days during a week within the Treatment Period will be considered a non-responder for that week. A patient will be deemed a weekly non-responder for all weeks following the patient's discontinuation from the study treatment.

Similarly, the weekly symptom score that is calculated using daily eDiary symptom assessments will be the average of available daily assessment records for at least 4/7 records during the relevant week. The weekly symptom score will be set to missing for weeks with fewer than 4 days of daily assessments. For patients who prematurely discontinues the treatment prior to Week 12, the weekly symptom scores will be considered missing for all weeks after the treatment discontinuation.

Unless stated otherwise, missing data will not be imputed.

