7.8.9.1. Key Efficacy Endpoints

Change from Baseline in Abdominal Pain Through the Treatment Period

The Change from Baseline in Abdominal Pain Through the Treatment Period is defined as the overall change from baseline in the Abdominal Pain through the Treatment Period, which is estimated based on each weekly change from baseline in the abdominal pain score (based on the daily abdominal pain at its worst score) minus the baseline abdominal pain score for patients in the mITT population.

The postbaseline weekly abdominal pain score is the average of the non-missing daily abdominal pain at its worst scores during a week (Weeks 1-12) if there are at least 4 daily scores entered into the eDairy during the week, or will be considered as missing if there are less than 4 daily scores in the week. Weekly change from baseline will be calculated for each week as the weekly score minus the baseline score.

6/12 Week Abdominal Pain 30% Responder

The 6/12 Week Abdominal Pain 30% Responder is defined for patients in the mITT population and is a patient who meets the Weekly Abdominal Pain 30% Responder criteria for at least 6 out of the 12 weeks of the Treatment Period. A Weekly Abdominal Pain 30% Responder is a patient who has a decrease from baseline of at least 30% in the weekly abdominal pain for that week. If a patient did not have an abdominal pain score for at least 4 days in a particular week during the Treatment Period, the patient will not be considered a Weekly Abdominal Pain 30% Responder for that week. For all weeks after the treatment discontinuation, the patient will be considered as non-responder. A patient in mITT population who did not have any post baseline assessment for abdominal pain at its worst will be considered a weekly non-responder for all post baseline weeks, subsequently, will not be a 6/12 week abdominal pain responder.

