7.8.9.2. Analyses of the Key Efficacy Endpoints

Change from Baseline in Abdominal Pain Through the Treatment Period

The overall treatment effect will be evaluated via the comparison between the MD-7246 dose groups and placebo with regard to the weekly change from baseline (CFB) in abdominal pain using a MMRM model, including the weekly CFB score in abdominal pain as dependent variable and treatment, visit week (categorical), and treatment-by-week as fixed effects, patient as a random effect, and the baseline value as a continuous covariate. An unstructured covariance matrix will be used for the MMRM analysis, unless the model does not converge, in which case the compound symmetry will be used.

In this MMRM, a patient in mITT population without any postbaseline abdominal pain score at its worse will be considered missing. For patients with postbaseline abdominal pain scores, at any particular week, if there are fewer than 4 daily scores available, the weekly change from baseline will be considered as missing. Weeks after the treatment discontinuation will be considered as missing.

Descriptive statistics for the overall treatment effect based on the MMRM model will include the least-squares (LS) mean difference between each MD-7246 dose and placebo, LS mean change from baseline for each treatment, their corresponding 95% CIs, and the p-values associated with the comparisons to placebo. In addition, LS Means for the weekly treatment differences between each MD-7246 group and placebo will also be provided with the same set of statistics derived from the same MMRM model defined above and will be plotted based on the MMRM estimates.

Additionally, the non-model based descriptive statistics for the corresponding change from baseline (overall or weekly) will be provided by treatment group in the same tables for the MMRM estimates. Among them, the overall change from baseline is defined as the average of all non-missing post baseline daily scores during the Treatment Period minus the baseline abdominal pain score. The cumulative distribution for the overall change from baseline during the entire treatment period will be summarized and plotted by treatment group.

6/12 Week Abdominal Pain 30% Responder

For the 6/12 Week Abdominal Pain 30% Responder endpoint, the proportion of responders in each MD-7246 treatment group will be summarized and compared to the proportion of responders in the placebo group using a CMH test. The number and percentage of responders,

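### Does the planned 80% power fail because it allows for no loss and describes a Week 12 t-test rather than the treatment-period MMRM?

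*SAP*

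**What the plan says.** SAP section 4, Protocol section 10.8 and the Protocol synopsis give one calculation: a difference of 1.0 in change from baseline to Week 12, a two-sided 0.05 level, a two-sample t-test, "an SD of 2.4, and 92 patients per treatment group (368 patients total), the estimated power is approximately 80" percent. The sentence before it reports that the SD in the earlier Phase 2b trial "ranged from 2.32 to 2.88".

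The 92 is the number randomised. The Protocol synopsis states "Approximately 368 IBS-D patients (approximately 92 patients per treatment group) will be randomized into the Treatment Period", and SAP section 3.4 agrees: "Approximately 368 patients will be randomized to 1 of 4 treatments". Protocol section 6.4 adds "Patients in this study who prematurely discontinue treatment will not be replaced". On incomplete diaries, SAP section 7.3 says "The weekly symptom score will be set to missing for weeks with fewer than 4 days of daily assessments", and scores after treatment discontinuation are also missing.

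The SAP's key continuous endpoint "is defined as the overall change from baseline in the Abdominal Pain through the Treatment Period" (section 7.8.9.1). Section 7.8.9.2 continues: "The overall treatment effect will be evaluated via the comparison between the MD-7246 dose groups and placebo", using an MMRM on the weekly changes with baseline as a covariate and an unstructured covariance matrix. Compound symmetry is the fallback if the model does not converge. The same model supplies the difference from placebo at each week (SAP section 7.8.9.2; Protocol section 10.4.2).

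**The concern.** Three features of the planning section invite criticism.

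- The number that must be analysed equals the number randomised. The plan expects some missing weeks but states no loss rate and no inflation.
- Power is shown at a single SD, 2.4, near the low end of the quoted range.
- The calculation is for one week, whereas the SAP's key contrast averages over twelve. Neither document gives power, a detectable difference or an interval width for that average.

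If the 80% depended on complete Week 12 data, the study could be less sensitive than its readers believe, and a flat result at a useful dose would be harder to interpret.

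**Working it through.** **Inputs from the documents.** Difference 1.0; SD 2.4 (quoted range 2.32 to 2.88); n = 92 per arm; two-sided 0.05; no multiplicity adjustment (SAP section 7.6).

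**Inputs assumed here, because the documents give none.** Loss rate; between-week correlation r; correlation of baseline with change; how the effect builds up over time.

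**1. Reproduce the stated figure.** SE = 2.4 × √(2/92) = 0.354. Noncentrality = 1.0/0.354 = 2.826 on 182 df. Exact power is 80.3% (91 per arm gives 79.8%). The statement is right, and 92 is the smallest n that reaches 80.0% at SD 2.4.

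**2. The t-test with loss or another SD.** Same formula with n analysed per arm:

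| n per arm (assumed loss) | SD 2.32 | SD 2.4 | SD 2.88 |
|---|---|---|---|
| 92 (none) | 82.8% | 80.3% | 64.9% |
| 87 (5%) | 80.7% | 78.0% | 62.5% |
| 83 (10%) | 78.8% | 76.1% | 60.4% |
| 74 (20%) | 74.0% | 71.2% | 55.5% |

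These rows treat a dropout as contributing nothing. The planned model does not.

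**3. The planned model, illustrated.** Let V = SD² × R, where R has 1 on the diagonal and r elsewhere, over 12 weeks. Let d be the proportion lost, with last observed weeks spread evenly over Weeks 1 to 11. Write V(k) for the first k rows and columns of V, with its inverse padded by zeros to 12 × 12. The information per arm is

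I = 92 × [(1 − d) V⁻¹ + (d/11) Σ V(k)⁻¹], k = 1 to 11.

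A between-arm contrast a has variance 2 a′I⁻¹a, taken on 2 × 92 × (1 − d) − 2 df. Baseline adjustment with an assumed correlation of 0.3 in size subtracts 0.3² = 0.09 from every element of R. The build-up case takes weekly effects of 0.25, 0.5, 0.75 and then 1.0, with mean (0.25 + 0.5 + 0.75 + 9 × 1)/12 = 0.875.

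At SD 2.4 and d = 10%:

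| Contrast | r = 0.5 | r = 0.7 | r = 0.9 |
|---|---|---|---|
| Week 12, unadjusted | 77.7% | 78.6% | 79.7% |
| Week 12, baseline-adjusted | 81.2% | 82.2% | 83.2% |
| Period average, constant 1.0, unadjusted | 96.7% | 90.8% | 83.8% |
| Period average, build-up 0.875, unadjusted | 91.3% | 82.0% | 73.1% |
| Period 95% CI half-width, unadjusted | 0.52 | 0.60 | 0.67 |
| Period 95% CI half-width, baseline-adjusted | 0.47 | 0.56 | 0.63 |

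The Week 12 contrast, which is what the sample-size section describes, stays at about 80%. At 20% loss it is 75% to 79% unadjusted and 78% to 83% adjusted over the same r.

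**4. How far a period-average figure would move.** With complete data the SD of a 12-week mean is 2.4 × √((1 + 11r)/12), which is 1.77 at r = 0.5 and 2.29 at r = 0.9. With 92 per arm, power is 97% to 84% for an average difference of 1.0. If the effect rises linearly to 1.0 at Week 12, the average is 6.5/12 = 0.54 and power is 54% to 36%. The answer is set almost entirely by inputs that the documents do not contain.

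**The case for a change.** The best case for a change runs as follows. The section gives a reader nothing on the contrast that the SAP puts first. With no multiplicity control and no sensitivity analyses (SAP sections 7.6 and 7.8.9.3), interpretation will rest on estimates and intervals, so an expected interval width would be useful. The choice of SD matters more than loss. At 2.88 the t-test has 65% power with no loss, and at 2.60, the midpoint of the quoted range, it has 73.7%. The MMRM does not rescue this: at 2.88 with 10% loss its unadjusted Week 12 contrast has 62% to 64%.

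Much of that stands as description. The 2.4 does lie towards the favourable end, no loss rate is stated, and the period average has no planning figure. Three things do not follow. The documents do not show that 2.4 is wrong, and they print the range beside it with every other input, so the sensitivity can be computed from the page. It is too strong to say that there is no room for loss: the plan says approximately 80%, and 87 analysed per arm still gives 78.0% even by the t-test. And the powered contrast is not foreign to the analysis, because Week 12 is one of the weekly differences from the same key model.

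**Conclusion.** The stated power is correctly calculated and is not shown to be undelivered. At SD 2.4 with an assumed 10% loss, the planned model's Week 12 contrast has about 78% to 83% power across r from 0.5 to 0.9, with or without an assumed baseline correlation of 0.3. This rests on equal weekly variances, compound symmetry, dropout spread evenly over the weeks and ignorable for the MMRM, and no further weeks lost to sparse diaries.

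What remains is missing detail about the period average. Filling it would change no estimate, analysis or patient number. A half-width computed without baseline adjustment for r of 0.7 to 0.9 would read 0.60 to 0.67. The same calculation gives 0.52 at r = 0.5, or 0.56 to 0.63 once the planned covariate is included at the assumed correlation. Printing one such range would present unsourced assumptions as expected precision. Editing Protocol section 10.8 would also need an amendment with IRB approval (Protocol section 13.1). For a Phase 2 dose-ranging study that SAP Appendix 1 calls hypothesis generating, the single t-test calculation is a fair planning simplification. An author revising the SAP for other reasons could show power over the quoted SDs (83% to 65% with no loss), but the plan does not need it.
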